5. To analyze the perceived satisfaction rates of the athletes, using the SF-12 questionnaire after the intervention.
6. Know the effective dosage of a specific protocol for the prevention of ACL injuries.

PICO Question

In soccer players with DKV... Does a specific training protocol reduce the risk of ACL injuries compared to the conventional program?

Study hypothesis

A comprehensive and specific 12-week training protocol for the 2023-2024 season will significantly reduce the risk of ACL injuries compared to conventional training for female soccer players with DKV.

METHODOLOGY

Ethical documents and prior registration

This study has the Authorization of the Ethics Committee of the Responsible Research Office of the Miguel Hernández University of Elche for the 2022/2023 academic year and will be registered as a clinical trial in the clinicalTrials platform.

Studio Design

The study is designed as a randomized and controlled, double-blind, unicentric and parallel group clinical trial protocol that will be carried out with the female players of Elche CF and Intercity CF in the province of Alicante. The recommendations of the SPIRIT guide³⁶ have been followed for the realization of this study. Annex I.

Before starting the study, they will be provided with a written informed consent that they must sign to record their intention to participate in it, being able to revoke it at any time and accepting the conditions that will appear in the document (Annex II). They will be randomly assigned to a conventional fitness training program or a specific training protocol for 12 weeks. This study will consist of 3 time measurement points, the first prior to the intervention, the second at the end of the 6-week period of intervention and the last at 4 weeks after its completion. The study schedule and flowchart are in Annex III and IV, respectively.

Participants

The recruited population will be formed by the 44 elite players (22 per team) with a federative record belonging to the first senior team of Elche CF and Intercity CF of the province of Alicante of the national women's football league during the 2023-2024 season, where three weekly training sessions of one hour each are carried out. Prior to the collection of data, permission will be requested from the Club and the coach of both teams to carry out the study at the Martínez Valero Stadium in Elche. In the same way,

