the recruitment will be carried out through a direct contact, as an interview, with the coach, the physiotherapist and the physical trainer of the participating teams.

Inclusion and exclusion criteria

The inclusion criteria will be:

- Football players registered and federated in the corresponding team.
- With an age range between 18 and 35 years.
- Minimum experience of one year playing football.
- With the presence of DKV.

The exclusion criteria will be:

- Previously injured subjects of ACL or other knee ligament injury.
- Subjects with a history of lower extremity injuries that have resulted in surgery during the six months prior to the study.
- Players with chronic illnesses that may affect test results.
- Subjects who practice other sports in the professional field.

Study variables and measurements

To record the number of injuries produced among the players of both groups at the end of the study and the frequency of weekly training, an Excel table will be used. The kinetics and kinematics of the lower extremities will also be analyzed with a motion capture system, surface EMG markers and a force platform. The LESS scoring system (Annex V) and the DVJ task will be used to identify the risk of injury during the jump-landing task and the presence of DKV among the players, respectively. In addition, we will measure their pre- and post-intervention satisfaction rates using the SF-12 questionnaire³⁸. Annex VI.

Sample size

An analysis was performed with Epidat 4.2 software to calculate the sample size required in the present study. A comparison of independent means will be performed and a standardized mean difference of 1, a significance level of 0.05, a 95% CI and a power of 90% will be considered, which determines a total sample size of 44 subjects, 22 in each group. It is necessary to consider an abandonment rate, so we will increase the sample by 10%. Therefore, the total sample size will be 48 women, 24 in each study group. Annex VII.

Randomization and blinding

Teams will be randomly assigned to one of the two groups in a simple manner and will be performed once subject selection has been completed. This assignment will be hidden and will be carried out by a person independent of the study. The randomization method will consist of the toss of a coin assigning "heads" to the intervention group and "tails" to the control group.

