The intervention will consist of performing 3 weekly training sessions for 12 weeks to reach a total of 36 sessions of 30-60 minutes each. The days that will be set for training will be Mondays, Wednesdays and Fridays, leaving a rest day between sessions to ensure adequate recovery and quality training. The physical trainers will have to agree so that the training load in both groups is very similar.

Next, we will proceed to detail the intervention that will be carried out in each of the two groups of this clinical trial:

Conventional fitness training group

The players who belong to this group will maintain the usual practice of football training, so no new intervention will be applied.

Training group with a specific ACL injury prevention protocol

This protocol is based on prevention programs that use a multifaceted approach, effective in reducing the risk of ACL injuries compared to those who used only one type of exercise^{14,21,34}. A wide variety of studies defend the importance of working the muscles of the trunk, hip and knee to prevent DKV^{23,28,30}. Therefore, lumbo-pelvic stabilization training (*core* stability) that includes motor stability and strengthening of the gluteal muscles, in addition to strengthening the lower limb itself, will lead to a significant improvement in neuromuscular control of the lower extremities and trunk in addition to producing a significant decrease in DKV and valgus moments^{10,18,20,24,29,30,32}.

The proposed exercise protocol will be designed taking into account the inclusion of three main components. Annex IX:

- Lumbo-pelvic stabilization exercises.
- Lower limb strengthening exercises.
- Integration exercises (plyometrics and balance).

The exercises integrated into the programme will be organised into three phases of implementation:

- **Phase 1** (adaptation - 1st month): Its objective is that the players learn and integrate new patterns while they train.
- **Phase 2** (Proficiency - 2nd month): Aims for players to master new patterns in a controlled environment.
- **Phase 3** (performance - 3rd month): Its objective is to perform exercises in situations as specific as possible and close to the demand and explosiveness of movements typical of the pitch.

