First, qualitative variables will be described with frequencies and percentages. For these variables, hypothesis tests will be performed using the Chi-squared test. On the other hand, quantitative variables will be expressed with median and interquartile range (IQR) or with mean, standard deviation and confidence interval (95% CI). It should be verified that the data follow a normal distribution with the Shapiro Wilk test to test this hypothesis. If it were not met, a nonparametric test such as the Mann-Whitney test would be performed. If, on the other hand, it follows a normal distribution, an ANOVA test will be carried out to contrast the mean difference and assess whether or not the results of the clinical trial have been significant. A level of bilateral statistical significance (limit for judging a result as statistically significant) of $\alpha = 0.05$ shall be established for all hypothesis contrasts. The data will be analyzed with the statistical program SPSS.

Budget estimate

The budget available for this study is limited to material costs, since we have the collaboration of the team of physiotherapists from several clinics in the province of Alicante. Therefore, we will select, from among those who are willing to collaborate, both the evaluating and sports physiotherapists for the study. In addition, they will provide much of the materials needed to conduct the study. If, on the other hand, the collaborating clinics did not have all the necessary material, the cost of more specific devices

such as the mDurance surface EMG (€ 5,500 approx.) and the BMS force platform (€ 3,000 approx.) should be included in the budget.

FUTURE EXPECTATIONS OF THE STUDY

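### The only allocation method described randomises two clubs, one per arm, so training and club effects cannot be separated, while sample size and tests assume independently randomised players

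*Combined protocol and SAP*

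**What the plan says.** All references are to the combined protocol and SAP.

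- **Randomization and blinding** gives the only allocation method: "Teams will be randomly assigned to one of the two groups in a simple manner". It adds "The randomization method will consist of the toss of a coin", with heads for intervention and tails for control. The number of tosses is not stated.
- **Participants** names two clubs: "The recruited population will be formed by the 44 elite players (22 per team").
- **Studio Design** says "They will be randomly assigned to a conventional fitness training program or a specific training protocol for 12 weeks". The pronoun may refer to the players, but no player-level list, sequence or stratification by club appears anywhere.
- **Sample size**: "A comparison of independent means will be performed and a standardized mean difference of 1", with alpha 0.05 and 90% power. This gives 22 per group, raised to 24 for dropout. No ICC or design effect is mentioned.
- **Statistical analysis** lists Chi-squared and Mann-Whitney tests and, for normally distributed data, "an ANOVA test will be carried out to contrast the mean difference". No club term or cluster adjustment is given, and the section does not say whether final values or changes are compared.
- **Intervention** describes the control arm as follows: "The players who belong to this group will maintain the usual practice of football training". It also says "The physical trainers will have to agree so that the training load in both groups is very similar".
- **Limitations** has five items. None concerns the comparison of one club with another.

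**The concern.** If teams are the unit allocated and there are two of them, arm and club are the same variable. Coaching, squad composition, match exposure and local training habits all differ between clubs, and the control condition is whatever the control club normally does. Matching training load removes at most one of these differences.

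Randomisation supports a causal reading because chance differences between arms average out over many independently allocated units, and the analysis can quantify what remains. With one unit per arm neither happens. An observed difference, or the absence of one, could be a club effect. Player-level p-values and confidence intervals would also be too optimistic wherever players in the same club resemble one another. The plan calls itself a randomised controlled trial and hopes to persuade coaches to adopt the programme, so the claim at risk is its main one.

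**Working it through.** **1. Reproducing the plan's figure.** Inputs from Sample size and Statistical analysis: SMD 1, two-sided alpha 0.05, power 90%.

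n per group = 2 × (1.960 + 1.282)² / 1² = 21.01, rounded up to 22, so 44 in total. Exact power of the two-sample t-test with 22 per group (noncentrality √(22/2) = 3.317, 42 df, critical value 2.018) is 0.8997. The arithmetic is right, but only with a design effect of 1, that is, independent players.

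**2. What two clubs can support.** Between-club degrees of freedom within arms = 2 clubs − 2 arms = 0, so between-club variance cannot be estimated. If one toss settles both teams (an inference), there are two possible allocations, and they give the same absolute difference. A two-sided randomisation test therefore always returns p = 1. If each team had its own toss, both would land in the same arm with probability 0.5.

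**3. Type I error of the planned player-level test.** Let n be the players per club. The true variance of the difference in means is 2 × [ICC + (1 − ICC)/n]. The test assumes 2 × (1 − ICC)/n. The ratio is F = 1 + n × ICC/(1 − ICC), and the true type I error is P(|t| > t_crit/√F) with 2n − 2 df. The ICC values are assumed. Because the 22 per team is counted before screening for dynamic knee valgus (DKV), n = 11 is shown as an illustration.

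| ICC | F, n = 22 | Type I error, n = 22 | F, n = 11 | Type I error, n = 11 |
|---|---|---|---|---|
| 0.01 | 1.22 | 7.5% | 1.11 | 6.2% |
| 0.05 | 2.16 | 17.7% | 1.58 | 11.2% |
| 0.10 | 3.44 | 28.3% | 2.22 | 17.7% |

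Simulation with n = 22 (400,000 runs) gave 7.5%, 17.7% and 28.3%.

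**4. Power of a valid test, if the ICC were known.** This test is hypothetical, because the trial cannot estimate the ICC. It shows how much information the design carries. Design effect = 1 + 21 × ICC; effective n per arm = 22/design effect; power at SMD 1 by normal approximation.

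| ICC | Design effect | Effective n per arm | Power |
|---|---|---|---|
| 0.01 | 1.21 | 18.2 | 85% |
| 0.05 | 2.05 | 10.7 | 64% |
| 0.10 | 3.10 | 7.1 | 47% |

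**5. A fixed club difference instead of an ICC.** Suppose the clubs differ by d SD in the analysed outcome for reasons unrelated to training. The planned test then rejects with noncentrality d × √(n/2). With n = 22 this happens in 16% of trials at d = 0.3 and 37% at d = 0.5. With n = 11 the figures are 10% and 20%. Both values of d are assumptions.

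**6. Power if players are allocated within clubs, with club as a factor.** With 22 per arm (41 df), power is 90% at SMD 1, 74% at 0.8 and 49% at 0.6. With 11 per arm (19 df), it is 60% at SMD 1.

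**The case against.** The strongest reply is that the plan may intend to allocate players. The Studio Design sentence follows directly on the people who sign consent, and allocation takes place after subjects have been selected. The flowchart is in an annex that the public text does not include, and it might settle the matter. This stands as a reason to ask, but not as a defence. The one method given names teams, and 22 per team equals 22 per group. At the least, the plan is unclear about its unit of allocation.

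Second, the sizes rest on assumed ICCs and club differences. That is true, and they are labelled so. A stable baseline difference would largely cancel if change were analysed, and baseline measurements are planned. But the analysis section does not commit to change, and differences in coaching or match exposure during the trial would remain. The confounding itself needs no ICC.

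Third, the power figures in step 4 do not describe the planned test. A simulation of that test at SMD 1 (22 per arm, 400,000 runs) rejects in about 88%, 83% and 79% of trials at the three ICCs. These rates come with the inflated type I error of step 3, so they are not valid power.

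Fourth, both squads share a league and a province, train three times a week, and would be measured by one blinded pair of evaluators. This narrows the differences between clubs without removing them. Keeping squads whole is also a recognised way to limit contamination. That is a fair reason to choose the design, but it does not justify analysing it as if players had been randomised.

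**Conclusion.** The concern holds and must be fixed. On the only allocation method described, treatment and club are completely confounded, and neither a different analysis nor more players from these two clubs can undo it. This conclusion depends only on there being two clubs and two arms. The stated 5% error rate and 90% power are properties of a design with independently randomised players. If outcomes are correlated within clubs, neither figure holds: the range is 7.5% to 28% type I error with 22 per club and 6% to 18% with 11, for assumed ICCs of 0.01 to 0.10. The one real uncertainty is whether the Studio Design sentence was meant to say that players are allocated. If so, the randomisation section is wrong and the individual-level calculation can stand.

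**What to change.** Make Studio Design and Randomization and blinding agree on the unit of allocation, then take one of two routes.

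**(a) Allocate players within each club.** Use a concealed permuted-block list stratified by club, and include club as a factor in the analysis. This needs no extra players and keeps the individual-level sample size calculation. The main cost is contamination, since team-mates in different arms can copy exercises. The plan offers little protection: the separate rooms divide interventions from measurements, not one arm from the other, and Limitations admits that supervision is intermittent. Dilution from SMD 1 to 0.8 or 0.6 lowers power from 90% to 74% or 49% with 44 eligible players, and with only 22 eligible in total power is about 60% even at SMD 1. Type I error stays at 5%, provided group delivery of the sessions does not itself create clustering. The claim that players are blinded becomes harder to sustain and would need restating.

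**(b) Keep the clubs whole.** Describe the study as a two-team controlled comparison and report estimates descriptively. Withdraw the stated alpha, the 90% power and the randomised causal claim, and add club confounding to Limitations. This costs only wording, but the trial gives up its confirmatory claim.

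Several clubs per arm, with a justified ICC and a cluster-level or mixed-model analysis, would also be valid. With 22 players per club, SMD 1, 90% power and a cluster-level t-test, that means 3, 4 or 5 clubs per arm at assumed ICCs of 0.01, 0.05 or 0.10, which is more clubs than the plan has.

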The study will have two physiotherapist evaluators, with at least five years of clinical experience. They will be responsible for the collection and analysis of data, assessments and evaluation of the final results. There will also be two sports physiotherapists, with at least five years of experience in the sports field, who will be responsible for the explanation and supervision of the exercises, in addition to being knowledgeable about the execution of specific training protocols.

A double-blind masking will be carried out, in which the evaluating physiotherapists and the players themselves will be blinded. Sports physiotherapists will be the only professionals who will not be. In addition, interventions and measurements will be performed in separate rooms, which will facilitate the blinding of subjects and evaluators.

Intervention

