This clinical trial protocol seeks to encourage coaches of women's soccer teams to follow this type of program because of its potential benefits in preventing ACL injuries. Annex X. Almost all the studies reviewed confirm that there are varied prevention programs (plyometrics, balance, strength, among others) that provide a significant improvement in DKV and, therefore, in the prevention of ACL injuries, but none of them has been based on a standard dosage or applied specifically to female footballers in this age range who have the highest injury rate^{5,14,19,21,34}. On the other hand, studies such as Willadsen et al.³¹ report short-term benefits and intervention programs that do not exceed 6-8 weeks of training¹⁴. The purpose of this study is to implement a standardized protocol for a period of 12 weeks (longer intervention time) in players of senior women's teams with the aim of achieving long-term benefits.

Limitations

- The study will be carried out only with female footballers of a specific age range, so that, when extrapolating the results, data such as the prevalence of ACL injuries could not be generalized to the entire population, so it would reduce external validity.
- We would not have all the control over the execution of the exercises described in the protocol, since the physiotherapists in charge of giving instructions would not be constantly controlling how each player performs the exercises, only at the beginning of the program or when introducing new exercises.

- To properly quantify the load, it might be more appropriate to do so with an accelerometer. It would serve to better control the exercise since, when the speed decreased, it would be indicative of stopping the exercise.
- As in almost any study, there is a risk of abandonment of the subjects, which increases with the duration of the study. Being a 12-week intervention, dropout rates could be higher.
- The relationship of the menstrual cycle in female footballers could be considered throughout the protocol, since there could be alterations in the performance and execution of the exercises¹¹.

Strengths

- Observer bias will be mitigated because measurements will be performed by two different physiotherapists. Both will not know the results of the other measurements made to prevent their expectations from influencing the result.

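### With one club per arm, separate rooms do not mask the evaluators: a single disclosure exposes the arm behind every later LESS score, and coded, identity-masked clips would protect LESS

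*Combined protocol and SAP*

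**What the plan says.** **Allocation.** Randomization and blinding states: "Teams will be randomly assigned to one of the two groups in a simple manner". It adds that "The randomization method will consist of the toss of a coin", and that allocation follows completion of subject selection. Participants names two clubs of 22 players each. Studio Design is looser: after describing what the players will sign, it continues "They will be randomly assigned to a conventional fitness training program or a specific training protocol for 12 weeks", which can be read as allocation of individuals.

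**Blinding.** Randomization and blinding claims masking of evaluators and players ("the evaluating physiotherapists and the players themselves will be blinded") and says that, among the professionals, only the sports physiotherapists are unmasked. The means offered is that "interventions and measurements will be performed in separate rooms, which will facilitate the blinding of subjects and evaluators". Under Strengths, a second safeguard against observer bias is that two physiotherapists measure: "Both will not know the results of the other measurements made to prevent their expectations from influencing the result".

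**Who knows what.** Under Intervention, the control club keeps its usual training and nothing new is added, while the other club has 36 programme sessions. That section also says: "The physical trainers will have to agree so that the training load in both groups is very similar". Weekly questionnaires on compliance with the programme are later analysed by the evaluators.

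**What is scored.** LESS is the measure named in specific objective 4 and is taken from the DVJ jump. The visual DVJ reading described under Intervention is the eligibility screen. The DVJ measure listed there for baseline is quantitative.

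**The concern.** Evaluator masking normally has to fail one player at a time. Here the allocation is one fact for the whole trial, namely which of two named clubs has the programme. The same two evaluators meet the players in person and may know their club from kit or face. A chance remark, a glimpse of training or a compliance questionnaire is then enough.

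LESS depends on a rater, and the protocol's Expected results section states the direction in which the programme club should change. A small expectation in the scoring would line up exactly with club and therefore with arm. Nothing in the data could separate it from a programme effect, yet the report would describe the assessment as blinded.

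**Working it through.** **1. Do the stated safeguards hide the club?**

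| Safeguard | What it hides | Hides club or arm? |
|---|---|---|
| Separate rooms (Randomization and blinding) | The training session | No |
| Ignorance of other measurement results (Strengths) | Other scores | No |

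The available text does not mention coded recordings, shuffled scoring, or a scorer kept apart from the players. The LESS and DVJ annexes (V and VIII) are not reproduced, so whether LESS is scored live or from video is unknown.

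**2. How far does one disclosure reach?** Assume that the evaluator knows who plays for which club.
- Allocation by club: one disclosure reveals the arm of 44 of 44 players.
- Allocation of individuals: one remark about one player reveals about 1 of 44.

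Only scores made after the disclosure are affected. The text does not say whether the coin toss comes before or after baseline measurement.

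**3. The plan's own sample size.** Inputs from Sample size and Statistical analysis: standardized difference 1, two-sided alpha 0.05, power 90%.
- n per group = 2 × (1.960 + 1.282)² / 1² = 21.01, rounded up to 22, so 44 in total. The stated 44 is reproduced.
- With 10% added: 44 × 1.10 = 48.4, against the stated 48.

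**4. Illustration of a scoring shift.** The shift b, in SD units, is an assumption; the documents give no figure. Take no true effect, 22 independent players per arm and a two-sided t test with 42 degrees of freedom. The noncentrality is b × √(22/2) = 3.317 × b.

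| b (SD) | Noncentrality | Rejection probability |
|---|---|---|
| 0 | 0 | 5.0% |
| 0.1 | 0.33 | 6.2% |
| 0.2 | 0.66 | 9.9% |
| 0.3 | 1.00 | 16.3% |
| 0.5 | 1.66 | 36.7% |

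**5. Why 5% is not the true starting point.** With one club per arm and within-club correlation ρ (also an assumption), the t statistic is inflated by √[(1 + 21ρ)/(1 − ρ)]. The critical value is 2.018, and there is no scoring bias.

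| ρ | Inflation | Rejection probability |
|---|---|---|
| 0.01 | 1.106 | 7.5% |
| 0.02 | 1.204 | 10% |
| 0.05 | 1.469 | 18% |

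The table in step 4 therefore shows how strongly a scoring shift acts on a nominal test. It does not show the error rate that better masking would restore.

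**The case against.** The case against has several parts.

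- **The visual DVJ is not exposed.** A reader might infer that it is. It is an eligibility screen read before allocation, so no arm exists to influence it. The DVJ outcome is described as quantitative, alongside motion capture, EMG and the force platform. This objection stands: on the visible text, LESS is the one landing outcome shown to depend on a rater's judgement.
- **Not every landing score is affected.** Scores fixed before a disclosure are safe. This stands.
- **Knowing the visit is harmless by itself.** Evaluators know whether a jump comes before or after training, but that applies equally to both clubs. Without knowledge of arm it does not bias the comparison between arms. This stands.
- **Coded clips do not restore the full claim.** A reader might infer that they make the trial double-blind. They cannot, because players know whether they received a new programme. This stands.
- **Knowledge of the allocation among club staff is inferred.** No sentence says that the trainers or coaches know it. For physical trainers the inference is strong, since they must agree load across the groups. For coaches it is plausible only. The conflict with the statement on unmasked professionals is therefore probable, not textual.
- **Allocation might be individual.** Studio Design can be read so. The explicit allocation text says teams, and the point rests on it.
- **Annex V may already specify video.** If so, part of the remedy is in place, but the text still needs coding, identity masking and a withheld key.

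None of these shows that club or arm is hidden from the evaluators.

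**Conclusion.** The point holds for LESS scores made after allocation. With teams allocated by one coin toss between two clubs, the stated safeguards do not conceal arm from the evaluators, and one disclosure exposes all 44 players from then on. This follows from the text and needs no assumed effect size beyond the evaluators being able to tell a player's club.

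The figures of about 10%, 16% and 37% are illustrative. They rest on assumed shifts of 0.2, 0.3 and 0.5 SD and on players being independent. A reader might take them to mean that proper masking would bring the false-positive rate back to 5%. The design does not support that: with any positive within-club correlation the rate is already above 5%, and masking leaves the confounding of club with arm untouched.

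The change is worth making because it replaces an ineffective masking method with a workable one at modest cost.

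**What to change.** 1. Replace the separate-rooms sentence with a scoring rule. Video-record the post-screening DVJ/LESS jumps at every visit, in neutral clothing with the face out of frame. The person independent of the study assigns random codes and holds the key until the scores are locked. After the last visit the same two evaluators score LESS, and any DVJ outcome rated by eye, from clips shuffled over clubs and visits. The screening DVJ is exempt, because it is needed at once to select players and precedes allocation.
2. State the limit: this protects LESS (with any eye-rated DVJ outcome), but not SF-12 or the injury record. It does not blind players or remove the confounding of club with arm. Drop the double-blind label for players.
3. Reconcile the statement that only the sports physiotherapists are unmasked with the physical trainers' task of agreeing load across groups. List everyone who will know the allocation.
4. Reconcile Studio Design with Randomization and blinding on whether players or teams are allocated.

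**Cost.** Protocol text, neutral clothing, some hours for coding and later scoring, and possibly an ordinary camera, since motion capture may not yield video fit for LESS. No added players, tests or assessors; the 44 and 48 stand. LESS scores would not be available on the day, and some recognition from build or movement may remain. The rule must be in place before measurement starts, because unrecorded jumps cannot be rescored.
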